### Patient demographics:

Variable	Role	Data source(s)	Operational definition	Time-point
Patient's biological sex	Primary objective	eCRF	Patient's biological sex	N/A
Patient's race/ethnicity	Primary objective	eCRF	Patient's race/ethnicity	N/A
Patient Hispanic/Latin/Spanis h origin	Primary objective	eCRF	Origin	N/A
Patient's BMI	Primary objective	eCRF	Patient's BMI at index	1 st dose of InO (index)
Date of patient's death (if applicable)	Primary objective	eCRF	Time since death	Anytime up to/including data collection
Primary cause of patient's death (if applicable)	Primary objective	eCRF	Primary cause of death	Anytime up to/including data collection
Is the patient actively being monitored or have they been lost to follow up?	Primary objective	eCRF	Patient lost to follow up	Anytime up to/including data collection
Last date of activity for this patient (if lost to follow up)	Primary objective	eCRF	Time since last date of activity/ time since lost to follow up	Anytime up to/including data collection

### **Clinical characteristics:**

Variable	Role	Data source(s)	Operational definition	Time-point
How many times has the patient received salvage therapy?	Primary objective	eCRF	Total number of salvage therapies received	Anytime up to/including data collection
On what date the patient received salvage therapy	Primary objective	eCRF	Date of each salvage therapy	Anytime up to/including data collection
Was the patient relapsed or refractory on receipt of this salvage therapy	Primary objective	eCRF	Relapse or refractory specification for each salvage therapy	Anytime up to/including data collection

Variable	Role	Data source(s)	Operational definition	Time-point
Duration of first remission following their ALL diagnosis before they relapsed? ( $\geq$ 12 months or <12 months)	Primary objective	eCRF	First remission duration	Since ALL diagnosis before relapse
Risk group of ALL based on cytogenic findings including: Philadelphia chromosome status, and cytogenetic, molecular and EMR positive	Primary objective	eCRF	Risk group of ALL at initial diagnosis	Initial ALL diagnosis, 1 st dose of InO (index)
ALL genetic alterations	Primary objective	eCRF	ALL genetic alterations at initial diagnosis	Initial ALL diagnosis, 1 st dose of InO (index
Laboratory test results	Primary objective	eCRF	Laboratory tests conducted at index	1 st dose of InO (index), After the last dose of InO prior to planned CAR- T infusion
Concomitant conditions	Primary objective	eCRF	Concomitant conditions present at index	1 st dose of InO (index)
ECOG performance status	Primary objective	eCRF	ECOG performance status at index	1 st dose of InO (index)
Patient diagnosed with veno-occlusive disease (VOD)	Primary objective	eCRF	Presence of VOD at any time	Anytime up to/including data collection
How was the patient diagnosed with VOD?	Primary objective	eCRF	VOD diagnosis	Anytime up to/including data collection
Did the patient receive defibrotide to manage their VOD?	Primary objective	eCRF	Defibrotide received	Anytime up to/including data collection
Most severe grade of VOD patient diagnosed with	Primary objective	eCRF	VOD grade at index	Anytime up to/including data collection
Bilirubin measured at most severe VOD diagnosis	Primary objective	eCRF	Measurement of bilirubin at most severe VOD diagnosis	Anytime up to/including data collection
Bilirubin level at most severe VOD diagnosis	Primary objective	eCRF	Level of bilirubin at VOD diagnosis	Anytime up to/including data collection
Platelet count measured at most severe VOD diagnosis	Primary objective	eCRF	Platelet count at VOD diagnosis	Anytime up to/including data collection
Platelet count at most severe VOD diagnosis	Primary objective	eCRF	Platelet count result at VOD diagnosis	Anytime up to/including data collection

Variable	Role	Data source(s)	Operational definition	Time-point
Diagnosis of neutropenic sepsis	Primary objective	eCRF	Diagnosis of neutropenic sepsis	Anytime up to/including data collection
Risk factors for VOD	Primary objective	eCRF	Presence of risk factors for VOD at index	1 st dose of InO (index), Last dose of InO, At CAR-T apheresis, At CAR-T infusion
EMD	Primary objective	eCRF	Presence of EMD at R/R ALL diagnosis	At R/R ALL diagnosis
Is the patient's EMD bulky (Definition: presence of a nodal mass with a maximal dimension of >10 cm, or mediastinal mass >1/3 maximum transverse diameter of the chest)	Primary objective	eCRF	Bulky EMD at R/R ALL diagnosis	At R/R ALL diagnosis
Sites of extra-medullary disease	Primary objective	eCRF	Location of EMD at R/R ALL diagnosis	At R/R ALL diagnosis
CNS disease	Primary objective	eCRF	Presence of CNS disease at R/R ALL diagnosis	At R/R ALL diagnosis
CNS disease status	Primary objective	eCRF	CNS disease status at R/R ALL diagnosis	At R/R ALL diagnosis

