#### Variables

The following variables will be captured within the electronic case report form (eCRF):

**Screener:** R/R B-cell ALL diagnosis, InO initiation (01 June 2017 onwards) as bridge to CAR-T, age at 1st dose of InO, patient currently (alive/deceased), 3 months follow-up data from 1st dose InO to last assessment, CAR-T completion status.

**Patient demographics**: biological sex, ethnicity, body mass index (BMI), date and cause of death, patient status (actively monitored/lost to follow-up).

Clinical characteristics: salvage therapy, R/R status, duration of first remission, ALL risk group/ALL genetic alterations (at ALL diagnosis; index), lab test results (index; after InO prior to CAR-T), concomitant conditions (index), Eastern Cooperative Oncology Group (ECOG) score (index), VOD diagnosis, treatment for VOD, grade of VOD, bilirubin and platelet level/count at most severe VOD, neutropenic sepsis diagnosis, VOD risk factors (index, last InO dose, CAR-T apheresis, CAR-T infusion), at R/R ALL diagnosis – extramedullary disease (EMD) diagnosis, sites of EMD, bulky EMD, central nervous system (CNS) disease.

**Patient treatments and clinical outcomes prior to CAR-T treatment**: current participation in clinical trial, treatments received, date of Blinatumomab initiation, Blinatumomab reason for use, Blinatumomab

PFIZER CONFIDENTIAL

Redacted

refractory status, date of InO initiation, total cumulative dose of InO, date Haematopoietic stem cell transplant (HPSCT) received, response to HPSCT, InO as bridge to HPSCT.

**Use of InO as bridge to CAR-T**: total number of InO cycles, InO receipt as inpatient/outpatient, date of InO initiation cycle 1, InO number and dose per cycle, InO best response (1st and last InO cycle), ECOG (last InO cycle), MRD (1st and last InO cycle), MRD assessment (1st InO cycle), MRD date (last InO cycle), MRD method (1st and last InO cycle), result of MRD analysis (1st and last InO cycle), InO prescribed as monotherapy/combination with chemo or other agent (1st and last InO cycle), dose of combination agent (1st and last InO cycle), date of final InO dose.

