
Due to the current paucity and lack of conclusive data demonstrating the use and outcomes of anti-CD22 antibody therapy ie, InO as a bridging therapy to CAR-T in ALL adult patients, particularly in the real-world setting, Pfizer would like to conduct a NI, chart review study to understand and describe the patient demographics, treatment patterns and clinical outcomes associated with InO when used as bridging therapy prior to CD19 directed CAR-T cell treatment. This study could elucidate to the clinical situations where InO can be used as well as potentially confirming the safety of this approach.

This NI study is designated as a PASS and is conducted voluntarily by Pfizer.

PFIZER CONFIDENTIAL

Redacted

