#### 9. RESEARCH METHODS

#### 9.1. Study Design

All assessments described in this protocol are performed as part of normal clinical practice or standard practice guidelines for the patient population and HCP specialty in the countries where this NIS is being conducted.

The following study will be managed by Adelphi Real World, acting as the Clinical Research Organisation (CRO) in collaboration with Pfizer. The protocol and study methods will be reviewed by principal investigators in the UK, US and Spain to ensure scientific and clinical merit. The study will be an international site-led (approximately 13 sites) retrospective observational chart review, assessing the characteristics and clinical outcomes of R/R ALL patients who received InO as a bridging therapy to CAR-T. Sites will be based in the US, UK, and Spain. Sites will be responsible for identifying eligible patients, electronic data abstraction and data query resolution. Clinicians and site staff will abstract data from adult R/R ALL eligible patients' medical records, with index defined as those initiating InO treatment as a bridge to CAR-T from index date 01 June 2017, and enter the required datapoints within an electronic data capture (EDC) system. Baseline patient demographics and clinical and molecular characteristics will be evaluated at index. Treatment patterns and effectiveness outcomes will be described throughout the follow-up period. Patients included will be required to have a minimum follow-up of 3 months defined as patients with 3 months of data following the first dose of InO to database extraction (patients who have died within 3-months of InO administration would be considered eligible for inclusion). See Figure 1 for the study schematic.

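### VOD and neutropenic sepsis are listed as undated ever/never events, and worst VOD grade is defined at index against its own row, so neither event can be placed relative to bridging InO

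*Protocol*

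**What the plan says.** In Section 9.3, under Clinical characteristics, VOD has the operational definition "Presence of VOD at any time" and the time-point "Anytime up to/including data collection". Seven further rows describe the VOD: how it was diagnosed, defibrotide use, worst grade, whether bilirubin was measured and its level, and whether platelets were counted and the result. All carry the same open time-point, and none is a date.

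The grade row names its variable "Most severe grade of VOD patient diagnosed with", keeps the open time-point, and then defines the variable as "VOD grade at index". Elsewhere in Section 9.3, index means the first dose of InO.

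Neutropenic sepsis is a single row, "Diagnosis of neutropenic sepsis", with the same open time-point and no date. The abstract's variable list agrees: "VOD diagnosis, treatment for VOD, grade of VOD, bilirubin and platelet level/count at most severe VOD, neutropenic sepsis diagnosis", again with no date.

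All these rows are assigned to the primary objective. Section 7 designates the study a post-authorisation safety study and gives "potentially confirming the safety of this approach" as part of its rationale.

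**The concern.** VOD and neutropenic sepsis are the principal toxicities listed for the period around InO and CAR-T. A reader of the report will want to know how often they occurred after bridging InO. An ever/never flag with no date does not answer that. It counts together an event after an earlier transplant or InO course, one during bridging, one after CAR-T infusion, and one after a later transplant.

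A missing onset date differs from a missing analysis rule: a statistical analysis plan can define windows, but it cannot assign an undated event to one. The grade row adds a second problem. A worst grade over all time and a grade at first dose are different quantities, and sites abstracting from the same row could record either.

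**Working it through.** The plan states no figure on this point. The expected 79 patients in Section 9.5 is a feasibility count. The check is therefore a comparison of the listed variables.

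**1. What is dated and what is not (Section 9.3)**

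| Item | Date listed? |
|---|---|
| Each salvage therapy | Yes |
| Blinatumomab, earlier InO and transplant before bridging | Yes |
| Bridging InO, first and final dose | Yes |
| MRD after InO | Yes |
| Leukapheresis, lymphodepletion, CAR-T infusion | Yes |
| Transplants after CAR-T | Yes |
| Death | Yes |
| VOD (eight rows) | No |
| Neutropenic sepsis (one row) | No |

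VOD risk factors are recorded at four time-points (index, last InO dose, apheresis, infusion). This dates the risk factors, not the VOD.

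**2. Periods an undated event could belong to**

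- Before index: Section 9.3 asks about earlier InO, an earlier transplant, and earlier InO as a bridge to transplant.
- Index to CAR-T infusion: the bridging period.
- After infusion.
- After a later transplant: Section 9.3 collects the number and dates of transplants after CAR-T.

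Where a patient has more than one of these exposures, dating the exposures does not place the event.

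**3. Length of observation**

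Index may fall any time from 01 June 2017, and data collection ends on 16 June 2025. The longest possible follow-up is therefore about 8 years (2025 − 2017). The minimum is 3 months, and patients who die or enter a CD19 CAR-T trial within that time may have less. Section 9.9 also expects data from infusion onwards to be embargoed for up to about 50% of patients in Spain, so for them the window in practice stops at infusion. A simple proportion over windows this unequal is not a risk over any stated period, and without dates it cannot be cut to a common one.

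**4. The grade row**

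- Variable: "Most severe grade of VOD patient diagnosed with".
- Time-point: "Anytime up to/including data collection".
- Operational definition: "VOD grade at index".

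The first two agree; the third does not. The neighbouring bilirubin and platelet variables refer to the most severe VOD diagnosis, which supports the first two.

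**The case against.** Several points on the other side stand and limit the conclusion.

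- **No safety endpoint.** The objectives in Section 8 contain no safety objective and no VOD incidence. Both events are descriptors under clinical characteristics, and the rationale is hedged. A reader might infer that the study's main safety endpoint fails; the protocol names no such endpoint.
- **The variable list is not final.** Section 9.3 leaves final variables to the finished CRF, which is not shown. A reader might infer that the dates are never collected; the documents support only that none is listed.
- **Adverse event reporting.** Section 11.1 sends adverse events that a healthcare provider has expressly linked to a sponsor drug to the CRF and the safety form. The form may carry onset dates to month and year, so some VOD cases could be dated this way. The route is partial: it requires a written causality statement, does not accept timing alone as a link, and yields no rate by window.
- **Not every patient is ambiguous.** For those with no earlier InO, no earlier transplant and no later transplant, the main competing periods do not arise. Events before and after infusion still cannot be separated.
- **The grade definition looks like a slip.** The same reference to index appears in the laboratory and VOD risk factor rows, whose time-points also run past index. It needs a wording correction and need not corrupt data.

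Two extensions are tempting but do not hold. Section 9.1 says "Baseline patient demographics and clinical and molecular characteristics will be evaluated at index", which might be read as contradicting the open windows. It concerns baseline characteristics only, and Section 9.3 does not confine its headings to baseline: date of death sits under demographics. The salvage count also runs to data collection, but its dates are listed, so it can be cut at index in analysis.

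**Conclusion.** The point holds as a gap in the listed data. VOD and neutropenic sepsis are undated over an open and unequal window, and one VOD row contradicts itself. As listed, the two proportions describe neither history at index nor occurrence after bridging InO. For patients with competing exposures, an analysis plan could not separate the two.

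The size cannot be calculated, because the documents give no expected number of events and no split by period. The share of recorded events falling in the bridging window is simply unknown.

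The conclusion assumes that the CRF follows Section 9.3 and adds no date fields. If the CRF already has them, only the grade definition and the reporting windows remain to be corrected. Even with dates, a single-arm chart review would show when events occurred, not that InO caused them.

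**What to change.** 1. Add an onset or diagnosis date for VOD and for neutropenic sepsis, queried only for patients recorded as having the event and before their eCRFs are locked.
2. Redefine the grade variable as the most severe grade from the first bridging InO dose onward, and record earlier VOD separately as history.
3. Tabulate both events by window: before index, index to CAR-T infusion, after CAR-T, and after a later transplant. Report the post-infusion windows only for patients whose data from infusion onwards are not embargoed, and state that denominator.

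The cost is two date fields, or one query round, on charts already being abstracted, plus table wording. Timing is the main drawback. Version 2.0 is dated 09 May 2025 and data collection is planned to end on 16 June 2025, 38 days later (22 + 16). Under Section 9.8, eCRFs that have been signed off are locked, and under Section 10.3 an amendment, if one is needed, requires prior ethics approval. The embargo also means that the later windows will be incomplete for part of the Spanish cohort whatever is changed.

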### Patient treatments and clinical outcomes prior to CAR-T treatment:

Variable	Role	Data source (s)	Operational definition	Time-point
Is the patient currently participating in a clinical trial other than a CD19 CAR-T trial?	Secondary objective: To describe InO treatment patterns in the study population, including chemotherapy regimen and dosage information	eCRF	Current clinical trial participation	At time of data collection

Variable	Role	Data	Operational	Time-point
		source (s)	definition	
Treatments received	describe InO treatment	eCRF	Treatments prior to InO as bridging therapy to CAR-	Prior to InO received as a
	patterns in the study		Т	bridge to
	population, including			CAR-T
	chemotherapy regimen and			
	dosage information			
At what date did this patient	Secondary objective: To	eCRF	Date received	Prior to InO
receive Blinatumomab?	describe InO treatment		(Blinatumomab)	received as a
	patterns in the study			CAR-T
	chemotherapy regimen and			CAR-1
	dosage information			
Did the patient receive	Secondary objective: To	eCRF	Reason for Blinatumomab	Prior to InO
Blinatumomab for MRD	describe InO treatment		tx	received as a
conversion, R/R disease,	patterns in the study			bridge to
frontline treatment or another	population, including			CAR-T
reason?	chemotherapy regimen and			
Was the patient refractory to	Secondary objective: To	eCRE	Was the nationt refractory	Prior to InO
Blinatumomah?	describe InO treatment	CCKI	to Blinatumomab ty	received as a
Dimutumoniuo	patterns in the study			bridge to
	population, including			CAR-T
	chemotherapy regimen and			
	dosage information			
At what date did this patient	Secondary objective: To	eCRF	Date received (InO)	Prior to InO
receive InO? prior to it being	describe InO treatment			received as a
received as a bridge to CAR-1	patterns in the study			bridge to
	chemotherapy regimen and			CAK-1
	dosage information			
Total cumulative dose $(mg/m^2)$	Secondary objective: To	eCRF	Total cumulative dose	Prior to InO
of InO received?	describe InO treatment		(InO)	received as a
	patterns in the study			bridge to
	population, including			CAR-T
	chemotherapy regimen and			
	dosage information	CDE		Duis a ta InO
At what date did this patient	describe InO treatment	eckf	(HPSCT)	received as a
	natterns in the study		(III SCI)	bridge to
	population, including			CAR-T
	chemotherapy regimen and			
	dosage information			
What was the patient's response	Secondary objective: To	eCRF	Response HPSCT	Prior to InO
to HPSCT?	describe InO treatment			received as a
	patterns in the study			bridge to

Variable	Role	Data source (s)	Operational definition	Time-point
	chemotherapy regimen and dosage information			
Has the patient been treated with InO as a bridge to HPSCT prior to InO as a bridge to CAR-T	Secondary objective: To describe InO treatment patterns in the study population, including chemotherapy regimen and dosage information	eCRF	InO bridge to HPSCT	Prior to InO received as a bridge to CAR-T
	Use of InO as a brid	lge to CA	R-T	
Number of cycles of InO treatment received	Secondary objective: To describe InO treatment patterns in the study population, including chemotherapy regimen and dosage information	eCRF	Total number of InO cycles received to date	InO received as bridge to CAR-T
Did the patient receive InO bridging to CAR-T therapy as an inpatient or outpatient?	Secondary objective: To describe InO treatment patterns in the study population, including chemotherapy regimen and dosage information	eCRF	InO bridging as inpatient/outpatient	InO received as bridge to CAR-T
Date of InO initiation (day 1 first dose for cycle 1)	Secondary objective: To describe InO treatment patterns in the study population, including chemotherapy regimen and dosage information	eCRF	Date of InO initiation	InO received as bridge to CAR-T
Number of doses of InO (show per cycle)	Secondary objective: To describe InO treatment patterns in the study population, including chemotherapy regimen and dosage information	eCRF	Number of InO doses per cycle	InO received as bridge to CAR-T
Dose of InO treatment (mg/m  , show per dose per cycle)	Secondary objective: To describe InO treatment patterns in the study population, including chemotherapy regimen and dosage information	eCRF	Dose of InO per dose per cycle	InO received as bridge to CAR-T
Patients' best response after InO treatment (show for first and last cycle)	Secondary objective: To describe relevant treatment effectiveness outcomes for the study population,	eCRF	Best response after InO 1 st and last cycle	InO received as bridge to CAR-T

Variable	Role	Data source (s)	Operational definition	Time-point
Patients' ECOG performance	including time-to-next treatment and survival Secondary objective: To	eCRF	ECOG status after last	InO received
status at InO treatment response evaluation (show at last cycle)	describe relevant treatment effectiveness outcomes for the study population, including time-to-next treatment and survival		cycle	as bridge to CAR-T
Whether MRD was assessed following InO treatment (show at first and last InO cycle)	Secondary objective: To describe relevant treatment effectiveness outcomes for the study population, including time-to-next treatment and survival	eCRF	MRD assessment conducted per InO after 1 st and last cycle	InO received as bridge to CAR-T
Date of MRD assessment following InO treatment (show for first and last InO cycle)	Secondary objective: To describe relevant treatment effectiveness outcomes for the study population, including time-to-next treatment and survival	eCRF	Date of MRD assessment per InO after 1 st and last cycle (if assessed)	InO received as bridge to CAR-T
Method used to assess MRD after InO treatment (show for first and last InO cycle)	Secondary objective: To describe InO treatment patterns in the study population, including chemotherapy regimen and dosage information	eCRF	Method used to assess MRD after InO 1 st and last cycle	InO received as bridge to CAR-T
Result of MRD analysis after InO treatment (show for first and last InO cycle)	Secondary objective: To describe relevant treatment effectiveness outcomes for the study population, including time-to-next treatment and survival	eCRF	Result of MRD test after InO 1 st and last cycle	InO received as bridge to CAR-T
Was InO prescribed in combination with chemotherapy, monotherapy and/or another combination agent eg tyrosine kinase inhibitor (TKI)? (show for first and last InO cycle)	Secondary objective: To describe InO treatment patterns in the study population, including chemotherapy regimen and dosage information	eCRF	Prescription of chemotherapy/monotherap y/other combination agent alongside InO treatment (1 st and last cycle)	InO received as bridge to CAR-T
Type of combination agent prescribed in combination with InO treatment (show for first and last InO cycle)	Secondary objective: To describe InO treatment patterns in the study population, including chemotherapy regimen and dosage information	eCRF	Combination agent type (1 st and last cycle)	InO received as bridge to CAR-T
Dose of combination agent prescribed in combination with	Secondary objective: To describe InO treatment patterns in the study	eCRF	Dose of combination agent (1 st and last cycle)	InO received as bridge to CAR-T

PFIZER CONFIDENTIAL

Redacted

Variable	Role	Data source (s)	Operational definition	Time-point
InO treatment (show for first and last InO cycle)	population, including chemotherapy regimen and dosage information			
Date final dose of InO received	Secondary objective: To describe InO treatment patterns in the study population, including chemotherapy regimen and dosage information To describe relevant treatment effectiveness outcomes for the study population, including time- to-next treatment and survival	eCRF	InO final dose	InO received as bridge to CAR-T

